We will collect the following demographics during initial screening visit: age, gender, education level, antiplatelets and anticoagulation therapy, statin therapy, NIHSS, pre-procedure modified Rankin Scale (mRS), employment, history of depression, use of antidepressant medications, history of hypertension, history of stroke/TIA, history of seizures, comorbid diseases, and history of head injury.

CTP protocol (adopted from Kamath et al; *Neuroradiology*. 2008 Sep; 50(9): 745–751; Bathla et al, *J NeuroIntervent Surg* 2019;0:1–5. doi:10.1136/neurintsurg-2019-014810):

CTP is performed in the radiology department using Siemens CT scanner. Images will be acquired on either a 128 slice (SOMATOM definition AS; Siemens AG, Forchheim, Germany) or a 192 slice (SOMATOM Force, Siemens AG) scanner.

18 French IV access is obtained. Then 40 ml bolus of iodine contrast (Isovue-370, iopamidol, 370 mg iodine/mL; Bracco Diagnostics, Princeton, New Jersey, USA) is administered into a vein using a power injector (Stellant D; MedRad Inc, Indianola, Pennsylvania, USA), with a 2 s delay between contrast injection and scan initiation. The acquisition parameters are 80 kV and 9.6 cm scan range. The radiation dose is 2 mSv. Data are acquired using the protocol recommended: with 4 scans 3 s apart followed by 15 scans 1.5 s apart, and another 9 scans 3 s apart, totaling 28 scans over approximately 60 s. We will utilize the software in the Siemens CT scanner in our radiology department [The Syngo software (Syngo.via CT Neuro Perfusion VB30; Siemens Healthineers, Erlangen, Germany)]. Initial post-processing using the vendor specified parameters to include initial motion correction, bone removal and brain segmentation, 4D noise reduction, and reference vessel and arterial input function detection. The software is programmed to use the central volume principle will apply the curve fitting by least mean squares to obtain mathematical descriptions of the time-density curves for each pixel. A closed-form (non-iterative) deconvolution that accounts for delay-related errors is then applied to calculate the mean transit time (MTT) map. The deconvolution operation requires a reference arterial input function (AIF). The cerebral blood volume (CBV) map is calculated from the area under the time-density curves. Cerebral blood flow (CBF) is calculated as the CBV/MTT ratio. In Syngo, infarct core/non-viable tissue (NVT) is defined as rCBF < threshold. Voxels not treated as NVT are classified as 'tissue at risk' (TAR) if Tmax > 6 s. MR was calculated as MR=(TAR+NVT)/NVT.

MRI protocol:

MR Image Acquisition MR imaging will be performed on a GE 750W 3T scanner using a 32-channel head coil. Anatomical images will include volumetric T1 MPRAGE (TI=900ms, TE=3ms, TR=3000ms, flip angle=10°, FOV=210x210x210mm, matrix=420x420x420, bandwidth= 244Hz/pixel, acceleration=4) and T2 CUBE (TE= 90ms, TR= 3000ms, echo train length=130, FOV=210x210x210mm, matrix=420x420x420, bandwidth= 488Hz/pixel, acceleration=4) sagittal scans with a 0.5 mm isotropic spatial resolution. The 1H MRS data will be acquired from voxels placed in the centrum semiovale in the ipsilateral side of COICA using a single-voxel semi-LASER sequence with the following parameters: TE=288, TR=4000ms, Voxel size = 20x20x20mm, Spectral Width=5000Hz, Vector size=4096, and NEX=32. Data will be collected with and without water suppression.

Volumetric Anatomical Image Analysis: The volumetric anatomical T1- and T2-weighted images will be analyzed using BRAINS AutoWorkup 72 that includes a FreeSurfer 22,32,33 module using Nipype 39. The default FreeSurfer pipeline will be updated to segment the brain and generate the cortical surface using a 0.5mm resolution for the reconstruction. The original images and the automated pipeline results will be checked for validity by a trained technician who is blind to subject status. Of primary interest for this analysis is the volume of the hippocampus and amygdala as generated by this pipeline

MRI-Spectroscopy (MRS) Analysis. The 1H MRS data will be analyzed using LCModel 77. The water suppressed and non-water suppressed data will be analyzed to generate absolute concentrations after performing phase and eddy current correction. We will obtain concentrations measurements for NAA, glutamate+glutamine (Glx), total creatine (Cr+PCr), total choline (tCho), and lactate from

the 1H data. Only metabolites with a Cramer-Rao lower bound of less than 20% will be included in further analyses. Lactate concentrations will be the primary metabolite of interest for this study.

MRI protocol for checking silent infarcts/strokes will contain the same sequences described previously in addition to adding T2 and SWI sequences. Each will add 2-3 minutes with a total of 4-6 minutes

All MRI images required by the protocol may be completed under sedative, if subject requests and PI deems them eligible.

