Patients with complete occlusion of cervical ICA on imaging studies (MRA or CTA) and confirmed with DSA, a history of TIA or stroke , increased MTT and/or TPP on CTP in the ipsilateral side of the occluded ICA specifically in the MCA territory when compared to the opposite unaffected hemisphere, all occlusion is due to atherosclerotic disease and MoCA < 26 or abnormal result on another test in the battery (abnormal defined as 1.5 SD below age/ gender/ education matched norms).

- Subjects without increased MTT or TPP on CTP may still be included in the unrandomized prospective observational 3rd arm.

Phase:

Phase 2

Description of

University of Iowa Hospitals and Clinics

Sites/Facilities Enrolling**Participants:**

Endovascular balloon angioplasty and stenting

[figure not shown]
Intervention:**Study Duration:**

[figure not shown]
5 years

[figure not shown]
Participant Duration:

12 months

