4 STUDY DESIGN

4.1 OVERALL DESIGN

Primary Hypothesis:

Revascularizing symptomatic chronically occluded cervical ICA (COICA) using endovascular techniques will significantly improve cognitive outcome.

Primary Objective:

To test the hypothesis that endovascular revascularization of COICA (via endovascular techniques) improves significantly cognitive function assessed by a specifically designed battery of 14 cognitive tests including the MoCA.

Secondary Objectivs:

To test the safety of endovascular revascularization of chronically occluded ICA.

Tertiary/Exploratory Objectives:

To test the hypothesis that subjects with symptomatic COICAs and mild/moderate cognitive dysfunction have the following biomarkers:

- A) increased MTT or TTP on CTP in the ipsilateral side of the occluded ICA specifically in the MCA territory when compared to the opposite unaffected hemisphere
- B) Presence of lactate and decreased Naa/Cr in the watershed area (specifically centrum semiovale) on 1H-MRI-spectroscopy, and
- C) Decreased size of the hippocampus and amygdala on MRI.

Primary endpoints:

Cognitive outcome at 12-month follow-up assessed mainly by a specifically designed battery of 14 cognitive tests including MoCA.

Secondary endpoints:

1. Safety: Occurrence of Stroke, Cerebral Hemorrhage, or Death

Exploratory endpoints:

Biomarkers:

- A) The presence/absence of lactate on 1H-MRI spectroscopy in centrum semiovale in the ipsilateral side of COICA;
- B) The change in size of amygdala and hippocampus in the ipsilateral side of COICA.
- C) Improvement/ normalization of MTT and/or PTT on CTP specifically in the ipsilateral MCA territory.
- D) subgroup difference (Gender)

Study Design:

This is a phase 2 randomized single-center open label clinical trial with randomization of 1:1 to either best medical management vs. best medical management and endovascular revascularization of COICA. Subjects who meet all inclusion criteria but have a normal CTP may be included in the unrandomized prospective observational 3rd arm.

Intervention: Surgical intervention - endovascular balloon angioplasty and stenting

Protocol:**Screening, Enrolling, & Randomization:**

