5 STUDY POPULATION

5.1 INCLUSION CRITERIA

- Age \geq 21
- Complete occlusion of cervical ICA on imaging studies (MRA or CTA) and confirmed with DSA
- History of TIA or stroke
- Increased MTT and/or TTP on CTP as defined as TMax threshold of $> 10\text{cc} > 4$ seconds in the territory of the occluded carotid specifically in the MCA territory when compared to the opposite unaffected hemisphere
- All occlusion is due to atherosclerotic disease
- MoCA < 26 and/or one abnormal test on the rest of the neuropsychological battery administered at screening
- Occlusion is class A or B using COICA classification
- Study team able to gain consent from subject or LAR
- 7. Failed best medical treatment (continued TIA symptoms despite medical management)

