5.2 EXCLUSION CRITERIA

- History of Moyamoya or Moyamoya like disease
- Tandem occlusion
- No evidence of increased MTT or TTP on CT perfusion \diamond

- Severe co-morbid diseases: renal insufficiency, end-stage renal disease, liver cirrhosis, COPD requiring home oxygen, terminal illness such as cancer, Parkinson disease or other neurodegenerative diseases, severe cognitive heart failure, seizures, debilitating stroke, mRS ≥ 3 .
- Short life expectancy due to cancer or other co-morbid diseases
- Class C or D on COICA classification [◊]
- Occlusion of the Common Carotid Artery
- Normal neuropsychological battery results [◊]
- Subject unwilling to participate in follow up and/ or unwilling to be randomized to surgery [◊]

◊ If subject meets any combination of these exclusion criteria, they may be applicable for the non-randomized third arm.

If a subject meets all criteria and is randomized to surgery their eligibility will be confirmed by 1 outside adjudicator. If this decision is not in agreement with the PI then a second adjudicator will review. Despite ruling, inclusion will be confirmed by two clinicians (PI and adjudicator or both adjudicators).

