9.4.3 ANALYSIS OF THE SECONDARY ENDPOINT(S)

The safety measures of occurrence of Stroke/TIA, cerebral hemorrhage, or death will be analyzed as frequency within the 30-day post-procedure period. Analysis will be done in aggregate of the events combined and individually using a Kaplan-Meier survival estimation with a Logrank test. Adjustment for age, etiology of ischemia, and side of occlusion will be done using a Cox Model Regression. A two-sided type I error rate of 0.05 will be used.

Analysis of the Tertiary/exploratory Endpoint

Tertiary/exploratory endpoints will be analyzed individually. The presence/absence of lactate will be estimated by a proportion and evaluated using a Fisher's Exact Test. The change in sizes of amygdala and hippocampus in the ipsilateral side of COICA will be using a T-Test of the difference. Improved and/or normalization of MTT and/or PTT on CTP specifically in the ipsilateral MCA territory will be analyzed using a T-Test.

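### In the randomised arms raised MTT/TTP holds by selection, and decreased hippocampal/amygdala size and decreased NAA/Cr have no reference in any planned test

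*Combined protocol and SAP*

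**What the plan says.** All references are to the combined protocol and SAP. Markers are lettered as in Section 4.1; the synopsis uses a different order. The documents write the second perfusion measure as TTP, PTT or TPP, and I read these as the same quantity.

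- **Objective (Sections 1.1 and 4.1).** "To test the hypothesis that subjects with symptomatic COICAs and mild/moderate cognitive dysfunction have the following biomarkers": (A) raised MTT or TTP in the MCA territory relative to the other hemisphere; (B) lactate and decreased NAA/Cr in the centrum semiovale; (C) decreased hippocampus and amygdala size.
- **Entry to randomisation (Sections 5.1 and 5.5).** "Increased MTT and/or TTP on CTP as defined as TMax threshold of" more than 10 cc beyond 4 seconds, "specifically in the MCA territory when compared to the opposite unaffected hemisphere". A MoCA below 26 or another abnormal test is also needed. Section 5.2 excludes from randomisation anyone with "No evidence of increased MTT or TTP on CT perfusion" or "Normal neuropsychological battery results".
- **Third arm.** "Subjects without increased MTT or TPP on CTP may still be included in the unrandomized prospective observational 3rd arm". Section 5.2 also opens this arm to subjects with class C or D occlusion, a normal battery, or unwillingness to be randomised or followed.
- **Spectroscopy (Section 4.1, MRI protocol; repeated in 8.1).** "The 1H MRS data will be acquired from voxels placed in the centrum semiovale in the ipsilateral side of COICA".
- **Volumes.** The anatomical T1 and T2 scans are volumetric over a 210 mm cube, and the pipeline output is not limited to one side. The listed endpoint is ipsilateral change.
- **Analysis (Sections 9.4.3 and 9.4.9).** Lactate: a proportion and Fisher's exact test. Volumes: "The change in sizes of amygdala and hippocampus in the ipsilateral side of COICA will be using a T-Test of the difference". Perfusion: a t-test of improvement or normalisation. NAA/Cr is not mentioned. Section 9.4.1 item 4 relates the exploratory markers to how cognition changes, without a model.

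**The concern.** The objective is a statement about what these patients have at presentation. The planned tests concern what happens to them afterwards. For one marker the statement is settled by the entry criteria. For two others the word *decreased* needs something to be decreased from, and the plan names no norm, cut-off, opposite side or control group.

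If the plan is followed exactly, the study will end without an answer on baseline atrophy or NAA/Cr, although scans that could address the first are already scheduled. A report that repeated the objective's wording could also present a feature of patient selection as a finding about perfusion.

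**Working it through.** **1. The plan's own sample size.** Inputs from Section 9.2: MoCA difference 2, SD 2, power 80%, dropout 10%; two-sided alpha 0.05 from Section 9.4.2.

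- Normal approximation: n per arm = 2(1.960 + 0.842)² × (2/2)² = 15.7, so 16 per arm and 32 in total.
- t-based: 16.7, so 17 per arm and **34** in total, as stated.
- Dropout: 34 / 0.90 = 37.8, so **38**, as stated.

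The number reproduces. It is set for MoCA; the documents give no sample size for the biomarker hypothesis.

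**2. Marker A.** The objective and the inclusion criterion use the same contrast: the occluded side's MCA territory against the other hemisphere. Its absence is an exclusion. Cognitive abnormality, the other half of the hypothesis, is also required. Among correctly enrolled randomised subjects the prevalence of A is therefore 38/38 = 100% by selection. No result in those arms could contradict the hypothesis, and there is no unimpaired group within them for comparison.

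**3. Objective against planned test.**

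| Marker | Objective asserts | Planned endpoint and test | Is the assertion tested? |
|---|---|---|---|
| A: MTT/TTP | raised at baseline | improvement or normalisation; t-test | No, true by selection in randomised arms; the endpoint itself is testable |
| B: lactate | present | proportion; Fisher's test, groups not named | Yes, presence can be estimated |
| B: NAA/Cr | decreased | none | No: ipsilateral voxel only, no norm, endpoint or test |
| C: hippocampus, amygdala | decreased | ipsilateral change; t-test | No: change over 12 months does not show that baseline size was reduced |

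**4. What a side-to-side comparison could detect.** For a paired t-test, the detectable standardised difference (mean side difference divided by the SD of the side differences) is roughly (1.960 + 0.842)/√n.

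- n = 34: 2.802/5.83 = 0.48; t-based **0.50**.
- n = 38: 2.802/6.16 = 0.45; t-based **0.47**.

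Both are for 80% power and two-sided alpha 0.05. Thirty-eight assumes that every randomised subject has a usable baseline scan and a unilateral occlusion; 34 allows for about 10% without.

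**5. The third arm as a reference.** Its size is not stated. Assuming 10, 20 or 30 subjects against 34 to 38 randomised, the detectable standardised difference is 1.02 to 1.03, 0.79 to 0.80, or 0.69 to 0.71. Only large differences would be detected, before allowing for the mixed reasons for entering that arm.

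**The case against.** The strongest reply is that the endpoints are sound and only the objective is loosely worded. Section 3 speaks of measurable biomarkers that are associated with the condition, and justifies them as markers of better perfusion and better cognition. Tests of change, and the association with cognitive change, fit that purpose. An abnormal baseline is needed before normalisation can be seen, so the perfusion entry criterion serves that endpoint. This stands for perfusion. It does not supply a test of baseline size or NAA/Cr, which Sections 1.1 and 4.1 state as part of a hypothesis.

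Four stronger readings are tempting, and the documents do not support them:

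- *The whole biomarker objective is untestable.* Lactate presence needs no size reference and has a planned proportion. Perfusion normalisation can fail.
- *The trial will report a guaranteed positive perfusion result.* No planned analysis reports baseline prevalence of raised MTT/TTP. The circularity lies in the hypothesis, not in a scheduled result.
- *Volumes are acquired only on the occluded side.* Acquisition is volumetric. The restriction is in the stated assessment, endpoint and test. Only spectroscopy is acquired on one side.
- *The third arm is a ready control group.* It can include CTP-normal or cognitively normal subjects, so marker A is not universal across the whole study. But Section 9 uses it in no comparison, its entry reasons are mixed, and the screening text in Section 4.1 describes spectroscopy only for subjects with abnormal CTP and abnormal cognition. The schedule does not exempt the third arm from MRI, but does not mention spectroscopy either.

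**Conclusion.** The point holds in limited form. In the randomised arms, raised MTT/TTP is a condition of entry and cannot be a tested hypothesis. Decreased hippocampal and amygdala size and decreased NAA/Cr have no reference in any planned test, and NAA/Cr has no endpoint or analysis at all.

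Severity is minor. The objective is tertiary and exploratory, and neither the cognitive nor the safety conclusion depends on it. Section 2.1 mentions go/no-go criteria for phase 3 but does not tie them to these markers.

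The conclusion on marker A rests on the entry criteria being applied as written. The view that perfusion normalisation is testable assumes follow-up CTP is done: Section 7.3 lists it, but the Section 1.3 schedule does not mark it at 6 or 12 months.

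**What to change.** 1. **Size.** Add a baseline paired comparison of ipsilateral with contralateral hippocampal and amygdala volume, in subjects with unilateral occlusion, from the T1/T2 scans already planned. The cost is analysis wording and reporting the second side. The limitation should be stated: this tests asymmetry, would miss shrinkage on both sides, and treats the opposite side as a fair reference.
2. **Perfusion.** Remove raised MTT/TTP as a hypothesis for randomised subjects and keep its normalisation as the endpoint. Make Sections 1.3 and 7.3 agree on follow-up CTP. Optionally, relate the baseline volume with Tmax above 4 seconds, as a continuous measure, to baseline MoCA and composite z. In the randomised arms both are range-restricted by the entry criteria, so a weak association there would be hard to interpret.
3. **NAA/Cr.** Either list it as an exploratory endpoint and analyse its association with baseline cognition, or take *decreased* out of the objective. Neither needs new data for randomised subjects.
4. **Third arm.** Say whether it receives spectroscopy. If it does, show its marker values descriptively by reason for entry; if not, leave it out of the spectroscopy objective.

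The cost is a short amendment to Sections 1.1, 3, 4.1, 9.4.3 and 9.4.9, with the schedule clarification. The sample size and the primary analysis do not change.

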1 PROTOCOL SUMMARY

1.1 SYNOPSIS

Title: Neurocognitive Impairment Assessment in Symptomatic Carotid Occlusion Recanalized Endovascularly

Study Description: This is a phase 2 randomized single-center open label clinical trial with randomization of 1:1 to either best medical management vs. best medical management and endovascular revascularization of COICA. The study will utilize best medical management and will randomize patients to endovascular balloon angioplasty and stenting.

- A third study group will be included that meet selected exclusion criteria. This group will not be randomized, only eligible for best medical management and prospective observation.

Objectives:

Primary Objective:

To test the hypothesis that endovascular revascularization of COICA improves significantly cognitive function assessed by a specifically designed battery of 14 cognitive tests including the Montreal Cognitive Assessment (MoCA).

Secondary Objective:

To test the safety of endovascular revascularization of chronically occluded ICA.

Tertiary/exploratory Objectives:

To test the hypothesis that subjects with symptomatic COICAs and mild/moderate cognitive dysfunction have the following biomarkers:

- A) Presence of lactate and decreased Naa/Cr in the watershed area (specifically centrum semiovale) on 1H-MRI-spectroscopy, and
- B) Decreased size of the hippocampus and amygdala on MRI.
- C) increased MTT and/or PTT on CTP in the ipsilateral side of the occluded ICA specifically in the MCA territory when compared to the opposite unaffected hemisphere.

Endpoints:**Primary endpoints:**

1. Cognitive outcome at 12-month follow-up assessed mainly by a specifically designed battery of 14 cognitive tests including the MoCA.

Secondary Endpoints:

1. Safety: Occurrence of Stroke, Cerebral Hemorrhage, or Death

Exploratory endpoints:**Biomarkers:**

1. Resolution/improvement of previously increased of MTT and/ or PTT (normalization of MTT/ PTT) on CTP specifically in the ipsilateral MCA territory.

2. The presence/absence of lactate on 1H-MRI spectroscopy in centrum semiovale in the ipsilateral side of COICA;

3. The change in size of amygdala and hippocampus in the ipsilateral side of COICA.

4. Subgroups: Gender difference

Age ≥ 21**Study Population:**

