9 STATISTICAL CONSIDERATIONS

9.1 STATISTICAL HYPOTHESES

Primary endpoints:

Cognitive outcome at 12-month follow-up assessed mainly by a specifically designed battery of 14 cognitive tests including MoCA.

Secondary endpoints:

1. Safety: Occurrence of Stroke/TIA, Cerebral Hemorrhage, or Death

Exploratory endpoints:

1. Biomarkers: A) The presence/absence of lactate on 1H-MRI spectroscopy in centrum semiovale in the ipsilateral side of COICA; B) The change in size of amygdala and hippocampus in the ipsilateral side of

COICA; C) improved and/or normalization of MTT and/or PTT on CTP specifically in the ipsilateral MCA territory.

Subgroups: Gender difference.

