9.2 SAMPLE SIZE DETERMINATION

To maximize success of the intervention, we will only enroll subjects with classification of A, B, or C. The current success rate for revascularizing types A & B using EVT is 100% and type C using the Hybrid technique is 80% making the success rate for the whole sub-cohort is 93%. Based on our preliminary data and others, the mean difference in the pre- and post-procedure MoCA score was between 5-8 points. Using two comparisons: A) comparison between intervention vs. best medical management and B) pre- and post-intervention for successful vs unsuccessful intervention. We pooled the data for these studies, and then used the lower and upper ends of the confidence interval calculated between the suggested groups for the trial (best medical management vs. intervention). Doing so, we will assume the difference between pre- and post-procedure MoCA score to be 2 points and standard deviation to be 2 points. Assuming $\alpha=0.05$; $\beta=0.8$; and power of 80%, then our total sample size needed is 34 (Table 2). Based on our previous clinical trial experiences, we anticipate maximum of 10% drop out. Given that, then total sample size needed is 38 subjects with 19 subjects in each group.

Sample size estimates: Total N						
MoCA Score	Difference in total points between pre and post procedure	1		2		3
		1	2	1	2	1
	Standard Deviation difference between pre & post procedure	1	2	1	2	1
	Power :					
0.8		34	128	5	34	6
0.85		38	146	12	38	8
0.9		46	172	14	46	8
0.95		54	210	16	54	8
						26

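### The 20% Cramer-Rao filter, applied to lactate, screens out low and absent values, and the plan has no rule for scoring lactate absent in the exploratory presence/absence endpoint

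*Combined protocol and SAP*

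**What the plan says.** The spectroscopy paragraph in section 4.1 (Overall Design), repeated in section 8.1 (Efficacy Assessments), sets the method: "The 1H MRS data will be analyzed using LCModel". It lists five measurements (NAA, glutamate plus glutamine, total creatine, total choline and lactate) and then sets the filter: "Only metabolites with a Cramer-Rao lower bound of less than 20% will be included in further analyses". The next sentence reads: "Lactate concentrations will be the primary metabolite of interest for this study".

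The endpoint, however, is binary. Section 9.1 gives it as "The presence/absence of lactate on 1H-MRI spectroscopy in centrum semiovale in the ipsilateral side of COICA", and the synopsis and sections 3 and 4.1 agree. It is listed as exploratory. Section 9.4.3 gives the analysis: "The presence/absence of lactate will be estimated by a proportion and evaluated using a Fisher's Exact Test". Section 9.4.9 repeats this.

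None of these sections exempts lactate from the filter, sets a detection limit, says how a failing lactate value is coded, or separates a poor spectrum from a good spectrum that contains no lactate. Sections 9.4.3 and 9.4.9 also do not say which visit or which comparison the Fisher test covers.

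**The concern.** A precision filter on a concentration normally removes unreliable measurements. Here the precision is expressed relative to the quantity being measured, so for a substance that may be truly absent the filter also acts on the outcome. A clean spectrum with no lactate gives an estimate near zero, a very large percentage bound, and exclusion. That spectrum is exactly the one that should count as absent.

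Two things are at stake. The proportion with lactate present would be pushed towards 100% wherever it is calculated. And the values lost would depend on the outcome: if the arms differ in how often lactate is absent, they would also differ in how much data they lose, so the test would compare selected subsets.

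**Working it through.** **Inputs from the documents.** Filter: bound below 20% (4.1, 8.1). Endpoint: lactate present or absent (9.1). Test: Fisher's exact (9.4.3, 9.4.9). Number randomised: 38, or 19 per arm (9.2).

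**The plan's own figure.** The only sample size given is for MoCA: "we will assume the difference between pre- and post-procedure MoCA score to be 2 points and standard deviation to be 2 points". A two-sample t-test with difference 2, SD 2, two-sided 0.05 and 80% power needs 16.7, so 17 per arm and 34 in total. Dividing by 0.9 for dropout gives 37.8, so 38. Both figures reproduce. They are used here only to fix the number of scans; the plan gives no power, prevalence, fitting error or detection limit for lactate.

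**Step 1: what the filter demands.** Let c be the lactate concentration and sigma its fitting error.

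percent bound = 100 × sigma / (estimated c)

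A bound below 20% requires estimated c > 5 × sigma.

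**Step 2: chance of passing.** Assume the estimate is normal around the true c with standard deviation sigma. Then P(pass) = P(Normal(c/sigma, 1) > 5).

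| True c/sigma | P(pass) |
|---|---|
| 0 | 3e-7 |
| 2 | 0.001 |
| 3 | 0.023 |
| 4 | 0.16 |
| 5 | 0.50 |
| 6 | 0.84 |
| 8 | 0.999 |

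True absences essentially never pass. Modest lactate mostly fails too.

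**Step 3: what remains.** Assume half the scans truly have lactate, at c/sigma = 8, and the other half count as absent. The share positive among retained values is P(pass | present) / [P(pass | present) + P(pass | absent)]:

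- absent at c/sigma = 0: above 99.999%
- absent at 2: 0.99865 / (0.99865 + 0.00135) = 99.9%
- absent at 3: 0.99865 / (0.99865 + 0.02275) = 97.8%
- absent at 4: 0.99865 / (0.99865 + 0.15866) = 86%

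The true share is 50% in every row. With absent meaning zero, about 19 of 38 lactate values would be retained (about 11 if true prevalence is 30%, about 27 if it is 70%).

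**Step 4: effect on the test.** Illustrative counts with lactate present, out of 19 per arm:

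| Present, arm 1 vs arm 2 | Fisher p, all scans kept | Fisher p, absent values dropped |
|---|---|---|
| 10 vs 3 | 0.038 | 10/10 vs 3/3: 1.0 |
| 9 vs 3 | 0.079 | 9/9 vs 3/3: 1.0 |
| 10 vs 4 | 0.091 | 10/10 vs 4/4: 1.0 |
| 8 vs 2 | 0.062 | 8/8 vs 2/2: 1.0 |

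The right-hand column follows automatically once every absent value is dropped. It shows the mechanism and is not separate evidence.

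**The case against.** The strongest reply is that the filter governs which concentrations are carried forward, and that a lactate value failing it is simply meant to be scored absent. The paragraph does speak of concentrations, and no section says how the binary endpoint is derived from them, so this reading is possible. It would keep the absent category. Two things still stand against it: the text does not state it, and it would score noisy or motion-degraded scans as absent, because the same bound also fails when sigma is large. Spectrum quality needs its own rule on either reading.

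Three stronger inferences are tempting, and the documents do not support them:

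- A reader might infer that whole spectra are discarded. The filter acts per metabolite, so NAA, creatine and choline from the same scan can stay.
- A reader might infer that the plan would lose its hoped-for result, clearance of lactate after revascularization. No such hypothesis is stated. The lactate objective in the synopsis is "Presence of lactate and decreased Naa/Cr in the watershed area", and the wording about resolution or improvement belongs to the perfusion measures. Section 3 does justify the biomarkers generally as markers of improved perfusion, and MRI is repeated at follow-up, so clearance is a plausible interest but remains an inference.
- A reader might take a fall from p = 0.038 to p = 1.0 as the measured loss. That is one assumed pair of counts; the three neighbouring pairs in the table are not significant even with all scans kept.

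It is also fair to say that the endpoint is exploratory, with no power attached.

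**Conclusion.** The point holds in a limited form. Read literally, the filter selects on the outcome and removes most or all of the absent category from the lactate endpoint, leaving Fisher's test little or nothing to compare. Read generously, the scoring rule is missing and poor scans would pass for absences. Either way the endpoint cannot be analysed as specified.

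The requirement of about 5 fitting errors follows from reading the bound as a percentage of the estimate. The pass probabilities add an assumption of normal error. How much is lost depends on prevalence and fitting error, which the plan does not give: under the cases worked above, a true 50% would appear as anything from 86% to nearly 100%. The p-values are illustrations only.

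The reach is confined to one exploratory endpoint. The primary MoCA analysis, the safety analysis, the sample size and the other metabolites are unaffected. It should be corrected, but it does not threaten the trial's main conclusion.

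**What to change.** Amend sections 4.1, 8.1, 9.4.3 and 9.4.9 as follows:

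1. Do not apply the 20% filter to lactate presence/absence. Keep it for concentrations of the other metabolites.
2. Judge spectrum quality independently of lactate, for example by linewidth and signal-to-noise, or by the bounds of NAA, creatine and choline on the same spectrum.
3. Score lactate present if it exceeds a prespecified detection limit, and absent if a good-quality spectrum does not reach it.
4. Treat only poor-quality spectra as missing, and report their number by arm.

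The cost is a few sentences. No new scans are needed, and the rule can be applied to spectra already acquired. The one real demand is that the detection limit must be fixed before the data are analysed.
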